2.0 Objectives*

2.1 Purpose, specific aims or objectives:

The overall objective of our study is to determine the clinical usefulness of BUS for NEC evaluation in diverse NICU settings. We plan to accomplish this overall objective by completing the following specific aims:

Specific aim #1: Determine the impact of add-on BUS for NEC evaluation on patient outcomes in two different NICU settings.

Specific aim #2: Determine the capability of implementing BUS for NEC evaluation in a level III NICU within an adult hospital.

2.2 Hypothesis:

Our hypothesis is that the addition of BUS to AXR can favorably change differential diagnosis, therapy plan, and patient outcomes of infants with suspected NEC; and that this beneficial impact extends to less specialized centers with little prior experience with BUS for NEC evaluation.

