Specific aim #2: To determine the capability of implementing BUS for NEC evaluation in a level III NICU within an adult hospital. We hypothesize that BUS timeliness, quality, and inter-rater reliability are comparable between level III and IV NICUs.

The addition of BUS to the diagnostic repertoire of infants with suspected NEC is an important contribution to neonatology. Before widespread adoption can be realized, however, strong evidence is needed to determine whether the addition of BUS would lead to actual clinical benefits, including in level III NICUs in adult hospitals. We anticipate that our study will help address this critical gap in knowledge and provide important insights as to the safe and effective use of BUS for NEC.

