28.0 Statistical Analysis*

28.1 We will use two-tailed McNemar's test with paired measures to analyze differences in diagnostic thinking efficacy and therapeutic efficacy from pre- and post-BUS surveys. Comparison of duration of antibiotics, bowel rest, and days to full enteral feeds will be performed using Student's t-test. Kaplan-Meier curve will be used to analyze time to full feeds between the 2 groups, censoring for death, discharge/transfer out of the hospital, or 30 days following initial NEC concern. Analyses of patient outcomes (duration of bowel rest, duration of antibiotics, time to full feeds) will follow the intention-to-treat principle, with statistical significance set at a P value of < 0.05.

28.2 We will use t-test to analyze differences in mean time of BUS image acquisition and reporting. Chi-square test will be used to compare differences in proportion of BUS studies that were performed and reported per standardized protocol. Inter-rater reliability for BUS studies will be assessed by Cohen's kappa statistics.

28.3 Sample size was calculated based on our pilot study which demonstrated a mean \pm SD of duration to full enteral feeds of 16 ± 9 days per episode of NEC concern. Using this information, we generated Table 1, which shows sample sizes for a range of possible means and standard deviations, with significance level of 0.05 and 80% power. For a 1-year study with 67 to 81 distinct episodes, for an SD of +8 days, we anticipate having sufficient sample size to detect a 5- to 6-day difference in mean duration to full feeds (highlighted in gray in Table 1).

Difference of means between groups	Expected Standard Deviation		
	± 8	± 9	± 10
4 days	126	160	198
5 days	81	102	126
6 days	56	72	88

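### The plan hypothesises benefit at the less specialised centre but pools patient outcomes and surveys over sites, so it yields no estimate of benefit at KUMC

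*Combined protocol and SAP*

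**What the plan says.** Aim 1 in section 2.1 is to "Determine the impact of add-on BUS for NEC evaluation on patient outcomes in two different NICU settings". The overall hypothesis in section 2.2 has two limbs: that adding BUS favourably changes diagnosis, therapy plan and patient outcomes, and that "this beneficial impact extends to less specialized centers with little prior experience with BUS for NEC evaluation".

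The analyses for aim 1 are in section 28.1:

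- Durations: "Comparison of duration of antibiotics, bowel rest, and days to full enteral feeds will be performed using" Student's t-test.
- Time to full feeds: "Kaplan-Meier curve will be used to analyze time to full feeds between the 2 groups".
- Surveys: McNemar's test, used to "analyze differences in diagnostic thinking efficacy and therapeutic efficacy from pre- and post-BUS surveys".

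None of these mentions site, whether as a stratum, a covariate, an interaction or a separate estimate.

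Sites are compared only under aim 2, whose hypothesis in section 1.0 reads "We hypothesize that BUS timeliness, quality, and inter-rater reliability are comparable between level III and IV NICUs". Section 28.2 gives the matching tests: "We will use t-test to analyze differences in mean time of BUS image acquisition and reporting", a chi-square test on adherence to the imaging protocol, and kappa. Section 28.3 sizes a single comparison of days to full feeds "with significance level of 0.05 and 80% power".

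**The concern.** The second limb of 2.2 is a claim about benefit at a particular kind of centre, and sections 1.0 and 3.1 give generalisability to level III units as a main reason for the trial. A comparison pooled over both sites estimates an average that CMKC dominates, because it is to supply 120 of the 200 neonates (section 8.0). That average can differ from zero while the effect at KUMC is nil.

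Section 32.0 makes unequal effects plausible. CMKC has paediatric imaging staff and has offered BUS for NEC since 2015. KUMC has mainly adult imaging staff, one radiologist with the expertise, and infrequent use. Most CMKC infants are transferred in, while most KUMC infants are born there.

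If the plan is followed as written, the report will contain no number from which a reader could judge whether infants at KUMC benefited.

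**Working it through.** **Inputs.** Total episodes are 67 to 81, the difference is 5 to 6 days and the planning SD is 8, with a pilot SD of 9 (all section 28.3). The enrolment goals are 120 neonates at CMKC and 80 at KUMC, 200 in all (section 8.0). Two assumptions are mine: KUMC supplies 80/200 = 40% of episodes, and arms are equal in size within each site. The documents state neither.

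**1. The plan's own figure.** Total N = 4 × [SD × (1.96 + 0.84) / difference]², two-sided. For 5 days and SD 8 this gives 80.4, against 81 in Table 1. The other eight cells also reproduce as totals for two arms, allowing for rounding. Table 1 therefore describes one pooled comparison, and nothing is sized by site.

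**2. Pooled result driven by CMKC alone.** With difference d at CMKC and zero at KUMC, the pooled difference is 0.6d, which is 3.0 days for d = 5 and 3.6 for d = 6. The pooled SE is SD × √(4/N). For N = 81 and SD 8 it is 1.78, so 3.0/1.78 = 1.69. The chance of a two-sided P < 0.05, by noncentral t, is:

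| Total N (SD 8) | d = 5 | d = 6 |
|---|---|---|
| 67 | 33% | 44% |
| 81 | 38% | 52% |
| 200 | 75% | 89% |

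This ignores the extra spread that unequal site effects create. Allowing for it, the variance becomes 64 + 0.6 × 0.4 × d²/2, which is 67.0 for d = 5 and 68.3 for d = 6. The 81-episode figures then become 37% and 49%. The conclusion is unchanged.

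**3. What KUMC alone could show.** The SE at KUMC is SD × √(4/n). The detectable difference is for 80% power by noncentral t, and the half-width is t × SE.

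| KUMC n | Detectable, SD 8 | Detectable, SD 9 | 95% CI half-width, SD 8 |
|---|---|---|---|
| 26.8 (40% of 67) | 9.0 days | 10.1 days | 6.4 days |
| 32.4 (40% of 81) | 8.1 days | 9.2 days | 5.7 days |
| 80 (full site goal) | 5.1 days | 5.7 days | 3.6 days |

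**4. Power of an arm-by-site term.** SE = SD × √(4/n at KUMC + 4/n at CMKC). For 81 episodes this is 8 × √(4/32.4 + 4/48.6) = 3.63, and 5/3.63 = 1.38, giving 28% power by the normal approximation. For 6 days the figure is 38%. With 67 episodes the two figures are 24% and 32%, and with 200 they are 58% and 74%.

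**The case against.** The strongest reply is that the plan does address generalisability. Aim 2 has its own hypothesis and its own tests, and the aim 1 hypothesis in section 1.0 contains no site contrast. This stands in part. A reader might infer that the plan never compares sites, or that no result could bear on one of its hypotheses. The documents do not support either reading: 2.2 is one compound hypothesis, its first limb is testable as planned, and the aim 2 measures are analysed in 28.2. The gap is confined to the second limb of 2.2, and to outcomes and surveys. Within that limit the reply fails, because timely, reliable imaging at KUMC would not show that infants there did better.

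A second reply is that KUMC's precision may not be poor. This also stands. The 40% share comes from the 200-neonate goal, and applying it to 67-81 episodes mixes two sample sizes. Addendum B adds a target of 80 infants and a 2-year study, whereas 28.3 speaks of one year. If all 80 KUMC neonates contribute, the detectable difference is close to the stated 5-6 days. To quote only 8-9 days would select the worst case.

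Third, a larger assumed effect at CMKC makes the problem look worse: 8.3 days there and none at KUMC gives a pooled 5.0 days and significance about 79% of the time with 81 episodes. That effect lies outside Table 1's 4-6 days and should not carry the argument.

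Finally, a reader might infer that the sponsor will present a pooled P value as evidence for KUMC. The documents state no such rule. They also state none that would prevent it.

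**Conclusion.** The point holds for the second limb of 2.2. No planned analysis of patient outcomes or of survey changes separates KUMC from CMKC, and the process measures cannot stand in for one. A 5-6 day effect confined to CMKC would still make the pooled test significant in roughly one third to one half of trials with 67-81 episodes, and in about 75-89% with 200. A larger sample therefore does not remove the ambiguity. It raises the chance of a pooled result driven by CMKC, while making the unplanned KUMC estimate more informative.

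The figures rest on a 60/40 split, equal arms within site and SD 8; at SD 9 the chance of a pooled result driven by CMKC is lower and KUMC's precision is worse. Allocation by birth month and repeat episodes per infant are ignored and would probably reduce power further. The pooled comparison itself is not called into question by this point.

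**What to change.** - **Section 28.1:** add the arm difference in days to full feeds at each site with a 95% CI, and an arm-by-site term. Label both as estimation. State that the interaction test has low power for a 5-6 day effect confined to CMKC: about 24-38% with 67-81 episodes and 58-74% with 200.
- **Section 28.3:** say that Table 1 applies to the pooled comparison only. Settle which sample is intended, then state KUMC's detectable difference for it. At SD 8 this is about 8.1-9.0 days if KUMC gives 40% of 67-81 episodes, or about 5.1 days if all 80 KUMC neonates contribute. At SD 9 the figures are 9.2-10.1 and 5.7 days.
- **Section 2.2:** state that the extension limb will be judged from the KUMC estimate and interval, not from the pooled P value. Alternatively, restrict that limb to the aim 2 process measures.

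The cost is some wording and one model term, with no extra infants and no change in care. The small downside is a less favourable and less precise statement about each site. At the smaller sample sizes the KUMC interval could seldom confirm or exclude a 5-6 day benefit, and the plan should say so in advance.

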3.0 Background*

3.1 Gaps in knowledge.

In reviewing the evidence supporting the use of BUS in the diagnostic imaging evaluation for NEC, several important limitations need to be considered. **First**, the best level of evidence regarding BUS for NEC has been limited to diagnostic accuracy studies. While appropriate for early investigation, diagnostic accuracy studies are insufficient in demonstrating the clinical utility of new diagnostic tests. **Second**, most of these diagnostic accuracy studies are small, single-center cohort studies that retrospectively assessed the authors' experience with BUS following its adoption into the diagnostic pathway for NEC. Such studies have limited power, are subject to numerous confounders and biases, and are meant to generate hypotheses that can then be studied via larger, prospective studies. **Third**, most of the prior research on BUS has been conducted in the level IV NICUs of free-standing children's hospitals with pediatric sonographers and radiologists. Most infants at greatest risk for NEC, however, are cared for in level III NICUs within adult hospitals staffed by adult sonographers and radiologists with little to no experience in how to perform and interpret BUS for NEC evaluation. This limitation raises the important question of generalizability beyond specialized pediatric centers.

 Children/Minors (under 7 years of age)	 Non-Viable Neonates (infants less than 30 days old)
 Children/Minors (7-17 years of age)	 Wards of the State
 Neonates (infants less than 30 days old)	 Fetuses
 Neonates of Uncertain Viability (infants less than 30 days old)	 Pregnant Women

SHORT TITLE: BUS for NEC

 Adults with impaired decision-making capacity	 CM Employees
	 CM Students/Residents/ Fellows
	 Economically or Educationally Disadvantaged Persons
	 Prisoners

- Neonates (infants less than 30 days old) will be included in the study as the peak onset of NEC in preterm infants is around 2 to 4 weeks of life. Thus, there is no other means to study the impact of BUS on infants with suspected NEC without including neonates. To assess potential risks of BUS in this vulnerable population, we reviewed the published clinical studies on BUS for NEC evaluation and confirm that BUS is safe and well-tolerated in this population. Furthermore, BUS is already used in clinical practice for the evaluation of NEC, and thus no added risk to the neonate will occur because of the proposed research.

8.0 Local Number of Participants

	Site 1 (CMKC)	Site 2 (KUMC)	Totals
Enrollment Goal: (Neonates) Number of participants to be enrolled = the number of participants to be consented or to be screened for chart reviews.	120	80	200
Enrollment Goal: (Neonatologists) Number of participants to be enrolled = the number of participants to be consented or to be screened for chart reviews.	120	80	200

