10.0 Procedures

10.1 Inclusion

Eligible infants who develop clinical concern for NEC for which the neonatologist decides to obtain imaging for further evaluation as part of usual clinical care will be included into the study.

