33.0 Multi-Site or Collaborative Research

Choose ALL relationship types that apply:

Multi-Site Research: Multiple sites will be engaged in this human research project. Sites will use the **same** protocol to conduct the **same** human research activities (except for minor variations due to local context considerations).

Collaborative Research: Multiple sites will be engaged in this human research project. Sites will **not** be performing the **same** research activities. The Site submission will specify the specific research activities each site will perform.

Student(s): Student(s) will help with this project and will be engaging their home institution.

Visiting Resident(s) / Visiting Fellow(s): Visiting Resident(s) / Visiting Fellow(s) will help with this project and will be engaging their home institution.

Complete the Chart (Add a new row for each site):

Site Name	Enrollment Goal for Site(s) Choose One	Relying on CM IRB?
KUMC	 Site will not rely on the CM IRB  If relying on the CM IRB: Site Enrollment Goal: 80 neonates and 80 Neonatologists  Site will not enroll	 External Site will rely on the CM IRB as the IRB of Record using a reliance agreement. (Required for non-Exempt NIH or other Federally Funded research)  External Site will utilize their home institution's IRB for IRB approval. A reliance agreement will not be sought.  Not Applicable. Site will not interact or intervene with human participants or their identifiable data / identifiable biospecimens.
UMKC	 Site will not rely on the CM IRB	 External Site will rely on the CM IRB as the IRB of Record using a reliance

	
 If relying on the CM IRB: Site Enrollment Goal: Click or tap here to enter text.
 
 Site will not enroll
	
agreement. (Required for non-Exempt NIH or other Federally Funded research)
 
 External Site will utilize their home institution's IRB for IRB approval. A reliance agreement will not be sought.
 
 Not Applicable. Site will not interact or intervene with human participants or their identifiable data / identifiable biospecimens.

--	--	--

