
The research could not practicably be carried out without the requested waiver/alteration (i.e., explain why the study could not be done if permission/assent/consent were required)
	
We initially conducted a pilot study to determine the feasibility of a RCT study design of BUS for NEC evaluation. While the RCT study design itself was feasible, we found that the process of obtaining consent was not practicable. The reasons why the proposed research could not be practicably carried out without the requested waiver are detailed below and in Fig 3:
 
(1) NEC is an emergency, making traditional parental consent at time of NEC concern impossible. Because NEC can rapidly deteriorate, infants with suspected NEC require “stat” evaluation with imaging and other laboratory tests. Families approached for research during emergency situations are often unable to give proper informed consent because of physical and emotional distress. Obtaining consent at time of NEC concern would also increase the risk of delaying evaluation. For these reasons, traditional parental informed consent at time of NEC concern is not possible for our study.
 
(2) Obtaining consent prior to NEC concern will require impractically large numbers to meet sample size demands. To overcome the emergency nature of NEC, we elected in our pilot study to seek consent from all infants who meet eligibility criteria, follow consented infants over time, and randomize only consented infants who develop concern for NEC. The problem with this approach is that only 36% (20/56) of consented infants developed NEC concern for randomization into the study. Based on these numbers, we will need to successfully consent 222 infants to achieve our target sample size of 80 infants. Although mathematically possible, it would require implausibly high approach and consent rates to successfully enroll 222 infants over the 2 years of the proposed study, making this approach of obtaining consent prior to NEC concern impracticable. This approach would also intrude on many families who would not need and may not

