(4) **Complexity of following consented infants for development of NEC concern result in missed randomization, loss of study participants, and insufficient power.** In our pilot study, 20% of consented infants who developed concern for NEC (4/20) were not randomized into the study. The complexity of following consented infants prospectively for development of NEC concern is a major contributing factor for missed randomization. This is because NEC concern, which by itself is already a relatively rare event, can occur at any time of the day or night, and can occur several weeks from the time of informed consent. The loss of even a few subjects from complex consent process and missed randomization would negatively impact the power and validity of our proposed study. Instead, we propose including all consecutive infants who develop NEC concern into the study with waiver of consent to simplify the study process, eliminate errors related to missed randomization, and maximize sample size and power for the study.

[figure not shown]

Figure 3. A hypothetical example of 100 eligible patients to demonstrate how traditional consent process prior to NEC concern is not practicable. Using estimates based on our pilot study, the traditional consent process would have only successfully randomized 13 infants (green box). The red boxes indicate reasons why the traditional consent process would not be practicable for our study. In contrast, a waiver of informed consent would have successfully randomized 36 infants (green box + yellow boxes).

SHORT TITLE: BUS for NEC

If the research involves using identifiable private information or identifiable biospecimens, the research could not practicably be carried out without using such information or biospecimens in an identifiable format	PHI is required to identify subjects and data from all participants is needed to describe aims of the study.

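### The plan's size figures (200 neonates, a target of 80 infants, 67 to 81 episodes) do not agree on either reading of the enrolment goal

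*Combined protocol and SAP*

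**What the plan says.** - **Section 8.0** gives 120 + 80 = 200 neonates and, in a parallel row, 120 + 80 = 200 neonatologists. Both rows carry the explanation "Number of participants to be enrolled = the number of participants to be consented or to be screened for chart reviews". The site chart in section 33.0 repeats the KUMC share: "Site Enrollment Goal: 80 neonates and 80 Neonatologists".
- **Addendum B** reports from the pilot that "only 36% (20/56) of consented infants developed NEC concern for randomization into the study", and concludes that "we will need to successfully consent 222 infants to achieve our target sample size of 80 infants". It places this in a study of two years. The caption of Figure 3 carries the same rate into the waiver design: per 100 eligible patients, "a waiver of informed consent would have successfully randomized 36 infants".
- **Section 10.1** brings into the study "Eligible infants who develop clinical concern for NEC for which the neonatologist decides to obtain imaging". Parental permission is waived for both arms (section 21.0 and Addendum B).
- **Section 28.3** uses a pilot mean and SD of 16 and 9 days to full feeds per episode. It assumes 67 to 81 episodes in one year and, at SD 8, claims a detectable difference of 5 to 6 days with 80% power at the 0.05 level.

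**The concern.** Three sizes are stated in three units: 200 neonates, 80 infants, and 67 to 81 episodes. Two durations are stated as well, one year and two. No sentence connects them.

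Because infant permission is waived, the only part of the section 8.0 explanation that can apply to infants is the screened part. Read that way, 200 is below the 222 that Addendum B calculates for its own target. Read as randomised infants, 200 is far above that target. A reader therefore cannot tell how many infants the comparison will rest on, or what difference it is designed to detect. Those are the figures on which the claim in section 28.3 depends.

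**Working it through.** **1. Reproduce the plan's figures.**
- Addendum B: 80 / 0.36 = 222.2, stated as 222. With the unrounded rate, 80 × 56/20 = 224.
- Table 1, two-sided 0.05 and 80% power, equal arms: total N = 4 × SD² × (1.96 + 0.84)² / d², with (1.96 + 0.84)² = 7.849 before rounding of the two terms.
  - SD 8, d = 5: 4 × 64 × 7.849 / 25 = 80.4 (stated 81).
  - SD 8, d = 6: 4 × 64 × 7.849 / 36 = 55.8 (stated 56).
  - SD 9, d = 4: 4 × 81 × 7.849 / 16 = 158.9, or 160 when rounded up per arm (stated 160).
- The other cells also reproduce. Table 1 therefore gives totals for both arms. The two-sided test and 1:1 split are assumptions, since the plan does not state them for this calculation.

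**2. Reading A: 200 screened eligible infants.**
- 200 × 0.36 = 72.0 randomised (200 × 20/56 = 71.4). This is 80 − 72 = 8 below target, or 10%.
- The exact 95% interval for 20/56 is 23% to 50%. Applied to 200, it gives about 47 to 99 infants.
- If the true rate is 36%, the binomial chance of 80 or more from 200 is about 13%.

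**3. Reading B: 200 randomised infants.**
- 200 / 80 = 2.5 times the Addendum B target.
- Two years at the section 28.3 rate: 2 × 67 = 134 to 2 × 81 = 162 episodes. Each randomised infant contributes at least one episode, so 200 infants need at least 200 episodes.

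**4. Power at each size.** Two-sample t-test, two-sided 0.05, equal arms, one episode per infant, no allowance for clustering by birth month. The noncentrality is (d/SD) × √(N/4); for example, N = 72, d = 5, SD 8 gives 0.625 × √18 = 2.65.

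| Total N | Difference | SD 8 | SD 9 |
|---|---|---|---|
| 72 | 5 days | 74% | 64% |
| 72 | 6 days | 88% | 80% |
| 80 | 5 days | 79% | 69% |
| 80 | 6 days | 91% | 84% |
| 200 | 4 days | 94% | 88% |

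Under reading A, the loss for 5 days at SD 8 is about 5 percentage points. Under reading B, the trial would have good power for 4 days, a smaller difference than section 28.3 claims.

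**The case against.** The explanation in section 8.0 looks like standard form wording: it appears unchanged in the neonatologist row. That row also favours reading B. Neonatologists take part by answering a survey after imaging, so equal goals of 200 fit one respondent per imaged infant better than 200 screened charts. This stands, although no passage says so, and it is why reading A cannot be treated as settled.

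The 36% is also a weak basis for a firm shortfall. It comes from 20 of 56 consented infants, a group that Addendum B believes over-represented healthier infants. A rate of 40% would give exactly 80 from 200. Figure 3 is labelled hypothetical, and the 222 was calculated for the consent route that the plan rejects. In the other direction, if some screened infants are ineligible, the yield falls. Further, 72 lies inside the 67 to 81 episodes of section 28.3, and repeat episodes (section 10.7) could raise the episode count. All of this stands and limits the size of the point.

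Three stronger readings are tempting but unsupported:
- **That a site stops accruing at its goal.** No such rule is stated. Section 9.3 takes consecutive infants over the study period, which suggests accrual by time.
- **That KUMC would randomise only about 29 infants (80 × 0.36).** The pilot rate is not site-specific. Section 32.0 describes mainly outborn infants at CMKC and mainly inborn infants at KUMC, so one rate need not hold at both.
- **That sections 9.3 and 10.1 contradict each other on who is included.** Section 9.3 refers to eligibility criteria that are not in the text available for this review, so the two may agree.

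**Conclusion.** The figures conflict as written, and neither reading of 200 removes the conflict. Reading A gives about 72 infants (about 47 to 99) against a target of 80, with a modest loss of power for 5 days and adequate power for 6 days at SD 8. Reading B overshoots the target by a factor of 2.5, exceeds what two years would yield at the stated episode rate, and leaves section 28.3 describing a different trial.

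The documents do not show that the trial is underpowered. They show that its size cannot be determined from them. The yield figures assume that all screened infants are eligible and that the pilot rate carries over to the waiver design. The power figures assume one episode per infant and independent observations. The mismatch between 200, 80, 222 and 67 to 81 does not depend on the power assumptions.

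**What to change.** - **Sections 8.0 and 33.0:** state the neonate goal, by site, as infants randomised at first NEC-concern imaging. Show the number screened as a separate figure.
- **Addendum B and section 28.3:** make the target and the study duration agree with that goal. At present one says two years and the other one year.
- **Section 28.3:** restate the expected number of infants, the expected number of episodes, and the detectable difference for that size.
- **If 80 randomised infants is kept:** set the screened figure at about 222 to 224 on the plan's own rate, which is 22 to 24 more than 200. Note that the rate is imprecise.
- **If 200 randomised infants is intended:** correct the target in Addendum B and base section 28.3 on 200.

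The cost is rewording and one restated calculation. Screening is by chart review under a waiver, so the extra charts add little work. The target does not need to rise.
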